12.1.3 Safety Assessments

This study will not involve the use of any clinical intervention or medications. Any adverse event that does occur will be reported on an adverse event form. The only expected risk to participants is a loss of confidentiality which will be minimalized by not obtaining signed informed consent and through anonymous data collection. Any breach of confidentiality will be reported on a protocol deviation form.

12.2 Training Procedures

All research staff will receive GCP training, protocol specific training, database training, and protocol specific assessment training applicable their specific roles and responsibilities before the study initiation. EMMES (NIDA DSC) will provide web-based training sessions for research staff at each site.

In addition, all research staff will complete site-specific training on human subjects research protection and receive certificates of completion.

13.0 STATISTICAL ANALYSIS

13.1 General Design

This study seeks to develop a 4-item screen (tobacco, alcohol, prescription medications, and other drugs) and a two-stage screening and brief assessment tool (called the TAPS Tool) that consists of the same 4-item screener followed by a brief assessment (using the modified ASSIST-lite). The screen and TAPS Tool will be evaluated for self-administration on an iPad and an interviewer-administered delivery.

Study procedures will include (a) pilot testing of the screen and TAPS Tool by 30 adult primary care patients to obtain feedback on their comprehension of the items and on the user-friendliness of the iPad version of the tool. Following review of the pilot data and possible modification of the screen and tool, participants will be administered the screen and tool via the two formats of administration (assigned at random) followed by a survey of comprehension, feasibility, acceptability, and preference for format of administration. Then, the RA will administer reference standard assessments.

13.1.1 Study Hypothesis

This study will not test any intervention or hypothesis. It will focus on the level of agreement between participants' responses to different sets of screening and assessment questions. Items that are considered to measure similar domains of substance use behaviors are expected to have a high level of agreement. The goal of the project is to develop and test a brief screen and the TAPS Tool. As such, the study is a measurement development project and so has no primary outcome variables.

It is expected that there will be no difference between positive responses on substance use between the self-administered screen or the TAPS Tool (delivered on an iPad) and the interviewer-administered screen and TAPS Tool.

It is expected that positive responses from the screen alone and on the TAPS Tool will show a high degree of agreement with well-validated screening and assessment measures.

13.1.2 Primary and Secondary Outcomes

The focus of this study is to identify a set of questions useful for detecting adults with use, subthreshold substance use disorder, and substance use disorder of tobacco, alcohol, prescription medications, and illicit drugs. As such, in a study of this nature, there are no primary or secondary outcome variables.

13.2 Rationale for Sample Size

To meet the goal of this study, the targeted sample size is expected to provide good precision of sensitivity and specificity of the screen and TAPS Tool when comparing to measures that are considered the gold standard (i.e., ASSIST and/or CIDI-SAM 2). To determine the most appropriate sample size, we performed simulations to calculate the precision of the estimates (specificity and sensitivity) as a function of prevalence and sample size. With a sample size of 2000 completers, we would have good precision of estimates (for sensitivity and specificity) on substances that are of moderate levels of prevalence (i.e., prevalence 5% or greater).

Based on prevalence estimates from a recently completed study in the adult primary care clinic of the New York City site, and known higher rates of prescription opioid misuse in the North Carolina sites, we anticipate having adequate precision to evaluate the tool's accuracy with respect to identifying sub-threshold SUD or SUD for the following substances: tobacco, alcohol, cannabis, cocaine, sedatives, heroin, and prescription opioids. For details regarding the sample size calculation approach see CTN-0059 Statistical Analysis Plan.

13.2.1 Projected Number of Sites and participants

The study will be conducted at primary care settings in three CTN Nodes: Mid-Atlantic Node (n = 800), Southern Consortium Node (n=800), and New York Node (n=400). However, the sites may continue to recruit competitively after they have reached their recruitment target until the entire study reaches 2,000 participants who have completed all of the assessments.

13.3 Statistical Methods for Primary and Secondary Measures

Statistical analyses will examine agreement between different measures of substance use (sensitivity, specificity, area under a receiver operating characteristic curve [AUC]) to evaluate the level of classification accuracy for each item or candidate combination of items. Considerations in determining the statistical approach can be found in the CTN-0059 Statistical Analysis Plan.

13.4 Exploratory Analyses

Exploratory analyses will be conducted to explore whether sensitivity, specificity, AUC differ as a function of factors such as gender, race/ethnicity, and education level. Exploratory analyses will also examine like combinations of substances (e.g., all opioids, all stimulants, illicit drugs other than marijuana, all prescription drugs) as described in the CTN-0059 Statistical Analysis Plan.

13.5 Missing Data and Dropouts

This study does not include follow-up assessments, and all study assessments will be completed during the visit. Missing data and dropouts are expected to be relatively minimal. Nonetheless, the analysis will determine the extent of missing data for all study variables and explore differences in missing data by age, gender, and race/ethnicity. No attempt will be made to impute missing data. The extent of missing data will be evaluated to determine their association with the mode of assessment.

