2.3 Study Population

This study will include a total of 2,000 adults recruited during their primary care visit in the study sites in three CTN Nodes (Mid-Atlantic, New York, and Southern Consortium Nodes). Only those recruited participants who complete the study will be counted toward to the total number of participants required for the study. Participants will be recruited by research assistants in the waiting room. An IRB-approved information sheet will be used to obtain verbal informed consent. Pending IRB approval of the protocol, written consent will not be obtained because the participant's name and signature would constitute the only recorded identifying information of the participant.

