6.2 Duration of Study and Visit Schedule

Following the pilot test, the study plans to recruit over a period of 10 months a total of 2,000 adults (ages 18 or older), who complete the study from all sites combined. Each participant will be seen only once for this study (no follow-up visits). Initial screening and all assessments will occur during the participant index visit. The total duration of individual participation in the study is expected to be from about 30 minutes to 1 hour (depending on how many substances they report having used).

Compensation:

To increase participants' retention to complete all assessments and to compensate participants for their time, each participant will be paid \$20 for completing the assessments and an additional \$10 for providing an oral fluid sample for drug testing.

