Informed consent will be obtained in a two-step process. In the first step, eligible patients who agree to participate in the study will be provided with an IRB-approved informed consent information sheet. The IRB will be asked to waive written informed consent because it is a minimal risk study, and the consent form would be the only place in which the name of the participant would be recorded. The information sheet will include a description of all significant elements of the study: the assessment interview and questionnaires; risks and benefits of study procedures; alternatives to participation in the study; confidentiality; \$20 payment for participation; a statement that participation is voluntary and that the patient may withdraw at any time; and information about whom to contact with questions. The consent form will also indicate that the decision to participate will in no way influence other aspects of the patient's treatment. Patients will read the first paragraph of informed consent information sheet (or have it read to them, if they are unable) and express verbally their understanding of the key elements of the study (e.g., random assignment, the approximate duration of assessments, and risks of participation).

After completing the assessments, participants will be asked to provide informed consent (using an IRB-approved consent form with waiver of written consent) to participate in the second step of the study in which they would provide an oral fluid sample for testing amphetamines, methamphetamine (including ecstasy/MDMA), cocaine/metabolite, opiates, oxycodone, phencyclidine, THC, barbiturates, benzodiazepines, and methadone. They would be told that drug testing data will be collected without a link to their name or other identifiers and that they are free to refuse to provide the sample. They will be informed they would receive an additional \$10 for providing the sample. Participants will not be asked to provide consent for the oral fluid

test until after they have completed all other study assessments in order to avoid biasing the self-reported data.

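### Oral fluid can be refused, but the missing-data section bars imputation and never compares missing samples with the screen/TAPS result or reported use, leaving the drug-use comparisons against oral fluid open to verification bias

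*Protocol*

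**What the plan says.** Section 13.5 (Missing Data and Dropouts) makes four statements that matter here:

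- On the amount: "Missing data and dropouts are expected to be relatively minimal".
- On handling: "No attempt will be made to impute missing data".
- On demographic checks, the analysis will "explore differences in missing data by age, gender, and race/ethnicity".
- On mode: "The extent of missing data will be evaluated to determine their association with the mode of assessment".

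Section 10.1 describes a two-step consent. The oral fluid request comes only after the other assessments are finished, and participants are told that "they are free to refuse to provide the sample". Sections 10.4 and 12.1.1 provide for people who stop there: $20 for the interview alone, $30 with the sample.

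Section 8.2 lists oral fluid as one of seven criterion measures, each used in separate analyses. Section 12.1.2 presents it as the biological, objective validation measure; the other six are interviewer-administered self-report.

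Sections 7.3 and 13.2.1 let sites keep recruiting "until the entire study reaches 2,000 participants who have completed all of the assessments". Section 2.3 adds: "Only those recruited participants who complete the study will be counted toward to the total number of participants required for the study". Section 6.1 includes oral fluid in the list of reference assessments.

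**The concern.** Section 13.5 fixes a rule on the premise that little will be missing, yet one criterion is missing by design for anyone who declines it. The request follows detailed questions about drug use, so refusal could plausibly be related to what the participant has just reported or chosen not to report. That is an inference. The protocol itself delays the request so that the prospect of testing does not distort self-report, which shows that it considers the two connected.

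Verification bias arises when the chance of having the criterion depends on the index result, or on the index result and true status together. The checks in 13.5 would not reveal this, because neither the screen/TAPS result nor reported use is among the comparison variables. The mode check is no substitute: each participant takes the tool in both modes before oral fluid is requested, so only the order differs.

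At stake is the one criterion that can expose under-reporting. A second, smaller issue is whether someone who declines the sample counts towards the 2,000.

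**Working it through.** **The plan's own figure.** Section 13.2 claims good precision with 2,000 completers at prevalence of 5% or more, without an interval width, so there is no stated precision to reproduce. For scale, 5% of 2,000 is 100 users. At an assumed sensitivity of 0.70 the 95% half-width is 1.96 × √(0.70 × 0.30 / 100) = 0.090, about ±9 points. At an assumed 20% prevalence (400 users) it is 1.96 × √(0.21 / 400) = 0.045.

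**Assumptions (not in the protocol).** True sensitivity s = 0.70, true specificity p = 0.85, and the sample-giving rates below.

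**Formulas.** Let v₁₁ and v₀₁ be the proportions giving a sample among users who test positive and negative on the tool, and v₁₀ and v₀₀ the same among non-users.

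- Complete-case sensitivity = s·v₁₁ / [s·v₁₁ + (1 − s)·v₀₁]
- Complete-case specificity = p·v₀₀ / [p·v₀₀ + (1 − p)·v₁₀]

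**Results.**

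| Who gives a sample | Sensitivity | Specificity |
|---|---|---|
| 95% of tool-positives, 99% of tool-negatives | 0.665 / (0.665 + 0.297) = 0.691 | 0.8415 / (0.8415 + 0.1425) = 0.855 |
| 75% of tool-positives, 90% of tool-negatives | 0.525 / (0.525 + 0.270) = 0.660 | 0.765 / (0.765 + 0.1125) = 0.872 |
| 60% of users who deny use, 90% of everyone else | 0.630 / (0.630 + 0.180) = 0.778 | 0.850 (unchanged) |

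The shifts in sensitivity are -0.9, -4.0 and +7.8 points. Each mechanism has a predictable sign: losing tool-positives lowers sensitivity and raises specificity, while losing users who deny use raises sensitivity. Refusal that depends on true status alone causes no bias (v₁₁ = v₀₁ and v₁₀ = v₀₀ cancel) but costs cases. The net sign is uncertain only when mechanisms combine.

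**What a correction recovers.** Take 2,000 people at 5% prevalence: 70 true positives, 30 false negatives, 285 false positives, 1,615 true negatives. That makes 355 tool-positives and 1,645 tool-negatives. The Begg-Greenes method applies the proportion of users among verified people to everyone with the same tool result.

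- *75%/90% case.* Verified: 52.5, 27, 213.75 and 1,453.5. Estimated true positives: 355 × 52.5 / 266.25 = 70. Estimated false negatives: 1,645 × 27 / 1,480.5 = 30. Sensitivity returns to 0.70.
- *Denied-use case.* Verified: 63, 18, 256.5 and 1,453.5. Estimated true positives: 355 × 63 / 319.5 = 70. Estimated false negatives: 1,645 × 18 / 1,471.5 = 20.1. Sensitivity is 70 / 90.1 = 0.777, almost the uncorrected 0.778.

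A correction based on the tool result therefore removes the first bias and leaves the second. Adding other self-reports would not help for people who deny use throughout, so that case needs a bound.

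**The case against.** **Scope.** Oral fluid is one of seven criteria, and its panel covers neither alcohol nor tobacco. For sub-threshold disorder and disorder, section 8.2 relies on the full ASSIST, the Fagerström test and the CIDI-SAM-2, and the precision argument in 13.2 rests on ASSIST and/or CIDI-SAM 2. This stands. A reader might infer that accuracy in general is exposed; optional sampling affects only the drug-use comparisons that use the sample.

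**Analysis set.** A reader might also infer that the plan analyses completers only. It does not say so. Sections 2.3, 7.3 and 13.2.1 govern who counts towards the recruitment target, section 8.2 has separate analyses per criterion, and section 13.3 leaves the approach to the SAP, which is not at hand. Barring imputation is compatible with using every available pair, so someone who declines the sample can still contribute elsewhere.

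**Dropout.** Visit length varies "depending on how many substances they report having used" (section 6.2). A reader might conclude that heavier users stop early. The passage concerns the number of substances, not heaviness of use, and nothing in the protocol shows early stopping.

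**Size.** The refusal rates are chosen, not documented. Anonymous testing and the extra $10 work against refusal. If missingness is minimal the shift is below 1 point, and every shift shown is within the ±9-point half-width at 100 users. This stands for rare substances. Bias does not shrink with more cases, however: at 400 users the half-width is 4.5 points, and an 8-point shift would exceed it.

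**The rule itself.** The sentence in 13.5 bars imputation, not weighting or a Begg-Greenes correction. This also stands, so it needs qualifying rather than deleting.

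**Completer.** Sections 6.2 and 10.1 use the word assessments as though the sample were separate, which would make someone who declines it a completer. Section 6.1 lists the sample among the assessments. The text supports both readings.

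**Conclusion.** The point holds as an inexpensive improvement to the drug-use comparisons that use oral fluid as the criterion. The protocol fixes a no-imputation rule and a list of missingness checks, makes this criterion refusable, and leaves out of that list the two variables needed to detect verification bias.

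With assumed true values of 0.70 and 0.85, the shift in sensitivity runs from under 1 point (95%/99% giving a sample) through -4 points (75%/90%) to +8 points (60% of users who deny use). The protocol states no refusal rate, so the actual size is unknown and could be negligible. The documents do not support extending this to a completers-only analysis, to accuracy against the other criteria, or to dropout among heavier users.

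Whether someone who declines the sample counts towards the 2,000 is unresolved in the text. If they do not count, recruitment would continue until people who consented to the sample made up the number.

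**What to change.** 1. In section 13.5, add a comparison of missing oral fluid by screen/TAPS result and by self-reported use to the checks already listed.
2. Qualify the no-imputation sentence. For oral fluid, report a verification-bias-corrected estimate beside the complete-case result, using Begg-Greenes or inverse-probability-of-verification weights based on TAPS, ASSIST, TLFB, CIDI-SAM, demographics and site. Add a bound for refusal that depends on true use, since weighting on self-report cannot correct for users who deny use. A stated range for the proportion of users among tool-negatives without a sample would serve.
3. Reconcile sections 7.3 and 13.2.1 with 10.1 and 12.1.1: define a completer as someone who completes the interview, with or without oral fluid. Those who decline then count towards the target and contribute to the ASSIST, CIDI-SAM and other self-report analyses.

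No new data collection is needed, because people who decline the sample have already completed the other assessments. The cost is revised wording, modest programming, a modelling assumption and slightly wider intervals for the corrected estimates.

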13.6 Demographic Characteristics

See Section 7.3.

14.0 REGULATORY COMPLIANCE AND SAFETY

14.1 Statement of Compliance

This study will be conducted in compliance with the appropriate protocol, current Good Clinical Practice (GCP), the principles of the Declaration of Helsinki, and all other applicable regulatory requirements. Participating sites must obtain written approval of the study protocol, consent form, other supporting documents, and any advertising for participant recruitment from their local institutional review board (IRB) in order to participate in the study. Prior to study initiation, the protocol and the informed consent documents will be reviewed and approved by an IRB. Any amendments to the protocol or consent materials must be approved before they are implemented. Annual progress reports will be submitted to each IRB, according to its usual procedures.

14.2 Regulatory Compliance

The regulatory files should contain all required regulatory documents, study-specific documents, and all important communications. Regulatory files will be checked at each participating site for the regulatory documents compliance prior to study initiation, throughout the study, as well as at the study closure.

14.3 Confidentiality

By signing the protocol signature page the investigator affirms that information furnished to the investigator by NIDA will be maintained in confidence and such information will be divulged to the IRB, affiliated institution; and employees only under an appropriate understanding of confidentiality with such board or committee, affiliated institution and employees. Participant records will be held confidential by the use of study codes for identifying participants on CRFs, secure storage of any documents that have participant identifiers, and secure computing procedures for entering and transferring electronic data. Based on communication with the NIDA certificate of confidentiality officer, this study will be conducted without a certificate of confidentiality because data will be collected anonymously and no contact information will be obtained because follow-up interviews will not be conducted.

14.3.1 Health Insurance Portability Accountability Act (HIPAA)

Protected health information will not be collected during the study.

14.3.2 Investigator Assurances

Each community study clinic site must file (or have previously filed) a Federal Wide Assurance (FWA) with the DHHS Office for Human Research Protection setting forth the commitment of the organization to establish appropriate policies and procedures for the protection of human research subjects, with documentation sent to NIDA or its designee. Research covered by these regulations cannot proceed in any manner prior to NIDA receipt of certification that the research has been reviewed and approved by the IRB provided for in the assurance (45 CFR 46.103(b) and (f)). Prior to initiating the study, the principal investigator at each study site will sign a protocol signature page, providing assurances that the study will be performed according to the standards stipulated therein.

14.3.3 Financial Disclosure

All investigators will comply with the requirements of 42 CFR Part 50, Subpart F to ensure that the design, conduct, and reporting of the research will not be biased by any conflicting financial interest. Everyone with decision-making responsibilities regarding the protocol will have an up-to-date signed financial disclosure form on file with their institution and follow other institutional requirements.

14.3.4 Inclusion of Women and Minorities

Women and minorities will be included in the study at all study sites.

14.3.5 Regulatory Files

The regulatory files should contain all required regulatory documents, study-specific documents, and all important communications. Regulatory files will be checked at each participating site for regulatory compliance prior to study initiation, throughout the study, as well as at the study closure.

14.3.6 Records Retention and Requirements

All records relating to this study will be retained for at least five years after completion of the research and will fulfill their IRB and sponsor record retention requirements. The five-year time period begins when the individual institution's engagement in the human subject research activity ends.

14.3.7 Informed Consent

The informed consent process is a means of providing information regarding the study to a prospective participant and allows for an informed decision about participation in the study. Because this study is minimal risk and data will be collected at only one visit and will be collected anonymously, only verbal consent will be obtained. However, IRB-approved informed consent information sheets will include all of the required elements of informed consent. Each study site must have the study informed consent information sheet approved by their IRB(s). A copy of the IRB-approved consent information sheet, along with the IRB study approval, must be sent to the Clinical Coordinating Center (CCC) and the Lead Node (LN) prior to the site initiation visit. Every study participant will be given a copy of the informed consent information sheet about the study and oral swab specimen collection.

Research staff who are knowledgeable about the study will explain the study to the potential participant and provide the individual with a copy of the consent information sheet to read. If the patient is interested in participating in the study, a research assistant who is authorized to obtain informed consent by the PI and if applicable by the IRB, will review each section of the informed consent information sheet in detail and answer any questions the participant may have. The participant will consent verbally. Persons delegated by the PI to obtain informed consent must be listed on the Site Staff Delegation of Responsibilities and Signature Log and must be approved by the IRB, if required. All persons obtaining consent must have completed appropriate training.

The informed consent information sheet must be updated or revised whenever important new safety information is available, or whenever the protocol is amended in a way that may affect participants' participation in the study. The participant will be informed that their participation is voluntary and they may withdraw from the study at any time, for any reason without penalty. Individuals who refuse to participate or who withdraw from the study will be treated without prejudice.

